6.5 RESPONSABILITYS OF SPONSOR AND INVESTIGATOR

The **Sponsor** (Drägerwerk AG) has the overall responsibility for the clinical trial including initiation, organization, and financing (according to the German Medical Device Act).

The sponsor and the clinical investigator assure that the clinical trial is performed in accordance with:

- DIN-EN-ISO 14155: 2011,
- Declaration of Helsinki concerning medical research in humans (Recommendations Guiding Physicians in Biomedical Research Involving Human Subjects, Helsinki 1964, amended Tokyo 1975, Venice 1983, Hong Kong 1989, Somerset West 1996, Edinburgh 2000, Washington 2002, Tokyo 2004, Seoul 2008, Fortaleza 2013).

This trial must be carried out in compliance with the protocol.

All investigators are licensed to practice medicine and have at least two years work experience in intensive care and anesthesia. All investigators have theoretical and practical experience in treating mechanically ventilated patients.

All investigators have theoretical and practical experience in conducting clinical trials and provide documented proof of GCP knowledge and/or investigator's training as well as knowledge of German Medical Devices Act.

The Coordinating investigator must have at least two years of experience in conducting clinical trials.

The investigator at each trial site is responsible for selecting and assembling the study team members (especially the medical staff) according to the requirements of this trial protocol. Furthermore, the investigator is responsible for training and supervision of the study team and providing all necessary information. This has to be documented.

6.6 MONITORING

The investigator agrees that the monitor will visit the trial site in appropriate intervals. During these visits the monitor will check the quality of the data recording and ensure that the trial site adheres to the timeframe as set in the study protocol. The investigators agree to provide any relevant information and documentation whenever the monitor requires that. This includes access to all original study documents and source data.

It is the responsibility of the investigator to keep the participant's chart as complete as possible (e.g. history, concomitant diseases, inclusion in the clinical study, visit dates, results of laboratory tests, distribution of the study medication, and adverse events). Source data are checked and compared with entries in the data bank. The participant has given consent with this procedure by signing the patient information and written informed consent form.

Tasks of the monitor and the quality assurance will be described in detail in a monitoring manual.

The monitor has the responsibility to treat all information confidentially and to safeguard the integrity and personal privacy of the study participants.

7 STATISTICAL CONSIDERATIONS

7.1 SAMPLE SIZE, DROP-OUT-RATES, LEVEL OF SIGNIFICANCE AND POWER OF THE CLINICAL INVESTIGATION

Primary Endpoint (Efficacy)

Based on former porcine trials⁷ with PulmoVista 500 and data from clinical studies with other EIT devices the sample size was calculated using the program G*Power 3.1.9.2.

An α -error of $p = 0.05$ and a power = 0.9 in a two-sided testing resulted in a sample size of 68 patients. With this sample size a difference of 0.1 of the mean cross-correlation coefficient shall be detected, i.e. the true value of a calculated mean of 0.8 will not be smaller than 0.7 and not be larger than 0.9 with the given p-value and power under the assumption of a standard deviation of less than .25.

Accounting for 15 % potential drop-outs 80 patients shall be enrolled in the study.

Secondary Endpoint (Efficacy)

Based on former porcine trials with PulmoVista 500 and data from clinical studies with other EIT devices the sample size was calculated using the program G*Power 3.1.9.2. An α -error of $p = 0.05$ and a power = 0.9 in a two-sided testing resulted in a sample size of 22 patients. With this sample size a difference of 0.1 of the proportion between reference and investigated variable shall be detected.

Accounting for 15 % potential drop-outs 25 patients shall be enrolled in this subgroup of the study.

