6.4.2.2 PATIENTS SCHEDULED FOR ELECTIVE SURGERY WITH OLV

Patients scheduled for elective surgery will receive medical care according to the hospital's established standards. Before anesthesia induction, study team will re-evaluate whether all in- and exclusion criteria are appropriately met (e.g. still intubated). Patients are considered "enrolled" when written informed consent has been obtained and all in- and exclusion criteria are appropriately met.

After arrival in the induction room, patients will be connected to the appropriate monitors for routine patient care. Additionally, patients will be asked to sit up and have the electrode belt of PulmoVista 500 fitted to their thorax according to the IfU. Investigational device is set up and connected to the patient and related devices.

Before and during pre-oxygenation of the patient, study personnel will start and test recording of the data. Anesthesia induction, placement and confirmation of correct placement of the DLT / bronchial blocker will be performed according to the hospital's established standards of care.

In patients who require independent lung ventilation during their surgical procedure, EIT measurements shall be performed during normal (both lungs) and single-lung ventilation after induction of anesthesia before start of surgery. According to standard of care correct positioning of the DLT respectively of the bronchial blocker will be tested by switching between normal ventilation and single-lung ventilation (right and left lung will be tested independently).

During the anesthesia induction, study personnel will note the time of particular events (e.g. start of induction, mask ventilation, intubation, clamping left/right) by using the clock on PulmoVista 500. The physician in charge of the anesthesia will be asked to allow uninterrupted baseline readings of at least 2 minutes after successful intubation and to keep the left and right lumen of the DLT clamped for at least 1 minutes each to ensure stable recording of the data. Each step of the testing of correct placement of the DLT or the bronchial blocker will be marked in PulmoVista 500 before the conduct of this step.

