7.2 STATISTICAL DESIGN

Null-Hypothesis

The PulmoVista 500 is not capable of continuously monitoring ventilation.

Primary Endpoint (Efficacy)

To assess the capability of PulmoVista 500 for continuous monitoring of ventilation and its changes at different points in time during varying states of regional ventilation, the cross-correlation function (CCF) between global tidal impedance (EIT) waveforms and global tidal volume (ventilator) curves will be evaluated.

- To refute the null-hypothesis of this trial it must be shown that the global tidal impedance waveforms and the global tidal volume curves correlate

⁷ Fischer E, Gremse F. Assessment of the capability of PulmoVista® 500 to continuously monitor regional ventilation distribution and its changes over time. An Animal Study. FINAL STUDY REPORT. PulmoVista 500-30022. Aix Scientifics. 2016-01-27

significantly, i.e. that the correlation scores are significantly different from zero.

- If the null-hypothesis is refuted the capability of PulmoVista 500 is assumed to be a valuable diagnostic device for long-term monitoring of mechanical ventilation.

The mean value of the intra-subject cross-correlation function (CCF) between global impedance (EIT) waveforms and global volume (ventilator) curves will be determined.

Secondary Endpoint (Efficacy)

To assess the capability of PulmoVista 500 to detect regional changes of ventilation it shall be tested, whether EIT can correctly differentiate between normal and single-lung ventilation.

- To refute the null-hypothesis of this trial it must be shown that the regional information about tidal impedance variation matches the clinical changes from normal to single-lung ventilation, i.e. that EIT detects ventilation vs. no ventilation in each lung.
- If the null-hypothesis is refuted the capability of PulmoVista 500 is assumed to be a valuable diagnostic device for detecting regional ventilation changes during long-term monitoring of mechanical ventilation.

The diagnostic output of the EIT measurements will be compared with clinical ventilation settings in a 2x2 table.

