7.3 PASS/FAIL CRITERIA

There is no pass/fail criteria defined.

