5.6 SECUNDARY ANALYSIS

5.6.1 Efficacy

- To demonstrate the ability of PulmoVista 500 to visualize regional ventilation changes, a quantitative evaluation is performed by calculating the cross-correlation coefficients between the impedance waveforms of PulmoVista 500 and the ventilator volume waveforms of OLV patients. The evaluation is carried out as in the primary analysis.
- In addition, a qualitative evaluation of the regional changes will be carried out. To do so, three blinded raters compare the corresponding sections of all OLV patients independently. Based on the information from the PulmoVista 500 video sequence provided, the raters evaluate which of the two halves of the lung is ventilated. The results are entered patient-related (pseudo-patient number) in the following table by the rater:

Pseudo-Patnr.	Valuation	
1	1	
2	2	
3	0	
4	1	
.	.	

Description of valuation:	0	not assessable
	1	right ventilated / left blocked
	2	left ventilated / right blocked

Tab. 1: Example of table for the qualitative evaluation of the OLV patients and the associated rating

The PulmoVista 500 video sequences to be assessed are created according to a workflow (see Appendix 7.3 Workflow for the creation of OLV videos) and made available to the raters. The pseudo-patient numbers are randomly generated by lot. These three tables of the raters will be merged into the KKS. A decision is considered positive or negative if at least two raters have come to the same result. In the opinion of one or more raters, is it not possible to judge the waveform (Code 0), the following assignment applies:

1x not evaluable & 2x same decision -> clear assignment in the table,
 1x not assessable & unequal decision of the remaining 2 raters -> drop out,
 2x or 3x not evaluable -> drop out.

A 2x2 Table will be created in the following form from the 3 tables of the raters (one of each rater):

Reference	Evaluation of the raters (with information provided by PulmoVista 500)	
	right ventilated / left blocked	left ventilated / right blocked
right ventilated / left blocked	a	b
left ventilated / right blocked	c	d

Tab. 2: Table for the accordance of rater and reality of the OLV patients

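### Protocol 7.1 claims 90% power to detect a 0.1 difference with 22 OLV patients, but 7.2 needs a match and the SAP plans intervals, so the figure does not say what the subgroup can show

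*Protocol*

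**What the plan says.** Protocol 7.1 (Secondary Endpoint) reports a G*Power calculation with alpha 0.05 two-sided and power 0.9, giving 22 patients. The effect is described only as: "With this sample size a difference of 0.1 of the proportion between reference and investigated variable shall be detected". It continues: "Accounting for 15 % potential drop-outs 25 patients shall be enrolled in this subgroup of the study".

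Protocol 7.2 says that to refute the null hypothesis "it must be shown that the regional information about tidal impedance variation matches the clinical changes from normal to single-lung ventilation", which it explains as showing "that EIT detects ventilation vs. no ventilation in each lung". The analysis is given as: "The diagnostic output of the EIT measurements will be compared with clinical ventilation settings in a 2x2 table". Protocol 7.3 adds: "There is no pass/fail criteria defined".

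SAP 5.6.1 makes this operational. Three blinded raters watch a video for each OLV patient, and "the raters evaluate which of the two halves of the lung is ventilated". A majority rule gives one result per patient. The success rate, sensitivity and specificity are then reported with confidence intervals. No interval method, test, null value or threshold is named. SAP 5.1 repeats only the 80 patients, the minimum of 25 OLV patients and the 15% drop-out rate.

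**The concern.** The power for a 0.1 difference between proportions depends strongly on where the two proportions lie, and Protocol 7.1 gives neither. The primary calculation in the same section does state a mean, a difference and a standard deviation.

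The direction matters more. A reader will take power 0.9 as the chance of showing that EIT agrees with the clinical setting, because 7.2 ties a favourable conclusion about the device to refuting the null. A calculation built to detect a difference between EIT and its reference gives the chance of showing that they disagree. Protocol 3.2 says that the results will support authorization in other countries, so a power statement that cannot be traced to the planned analysis is likely to be misread.

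**Working it through.** **Inputs.** From Protocol 7.1: n = 22, alpha = 0.05 two-sided, power 0.9, difference 0.1, drop-out 15%, 25 enrolled. From SAP 5.6.1: one result per patient. The proportions are not given, so every pair below is an assumption.

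**1. Reproducing 22.** Take an exact one-sample binomial test with reference 1.0 and true value 0.9. Any single failure rejects, so power = 1 − 0.9^n.
- n = 21: 1 − 0.9^21 = 0.8906
- n = 22: 1 − 0.9^22 = 0.9015

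So 22 is the smallest n that reaches 0.90. With equal tails, the any-failure rule at n = 22 needs a reference of at least 0.975^(1/22) = 0.9988. A scan of pairs 0.1 apart finds power of 0.90 or more only from a reference of 0.9989 upwards (or the mirror image, an error rate of about 0 against 0.1). An exact McNemar test with 10% discordance in one direction does not give 22: its power there is 0.018, and 91 patients would be needed.

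**2. What rejection shows in that reading.** Rejecting a reference of about 1.0 shows that agreement is below perfect. It is evidence of a shortfall, not of a match.

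**3. Power in the direction of a match.** Two-sided equal-tailed exact test, n = 22, upward rejection, 0.1 difference:

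| Null | True value | Power |
|---|---|---|
| 0.90 | 1.00 | 0 |
| 0.85 | 0.95 | 0 |
| 0.80 | 0.90 | 0.098 |
| 0.70 | 0.80 | 0.154 |
| 0.50 | 0.60 | 0.072 |

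Over nulls from 0.50 to 0.90 the maximum is at 0.8455. There 0.8455^22 is just below 0.025, so only 22/22 rejects, and power = 0.9455^22 = 0.29. An exact test that orders outcomes by likelihood has a maximum of 0.31. For 0.90 against 1.0, the upper tail at 22/22 is 0.9^22 = 0.098, so even a perfect result does not reject; 36 patients would be needed (0.9^36 = 0.0225).

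**4. What the planned intervals can show.** The SAP names no method; Clopper-Pearson is used here as an example. For n/n correct the lower 95% limit is 0.025^(1/n).

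| Correct / evaluable | Lower 95% limit |
|---|---|
| 22/22 | 0.846 |
| 20/22 | 0.708 |
| 21/21 | 0.839 |
| 19/21 | 0.696 |

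**5. Drop-out.** The primary calculation divides by 0.85: 68/0.85 = 80. The same rule gives 22/0.85 = 25.9, that is 26. With 25 enrolled, 25 × 0.85 = 21.25, so about 21 are evaluable. With 26, 26 × 0.85 = 22.1.

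**The case against.** **The pair 1.0 against 0.9 is a reconstruction.** This stands. The documents do not state it, and another reading also returns 22: a one-sample t-test on a 0.1 difference with an assumed SD of 0.1345 to 0.1379. The primary figure of 68 reproduces as that kind of test (0.1/0.25, power 0.902), and the designated first secondary endpoint in Protocol 6.1.3 is a cross-correlation. But 7.1 speaks of a proportion and gives no SD for this endpoint, and 7.2 plans a 2x2 table. The intended calculation cannot be settled from the documents, so a reader might infer, but cannot conclude, that the planners tested a perfect reference by mistake. The mismatch does not depend on the reconstruction: 7.1 itself describes detecting a difference from the reference, while 7.2 asks for a match.

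**Low power in the match direction depends on the test.** This stands too. At 22/22 against 0.90, the asymptotic likelihood-ratio statistic is 2 × 22 × ln(1/0.9) = 4.64 (p = 0.031), and the arcsine test gives z = 3.02. Both reject, so for 0.90 against 1.0 their power is 1.0. They are anti-conservative here, since the exact upper-tail probability is 0.098. The bound of about 0.3 therefore belongs to exact tests only.

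**The unit of analysis is given.** Correct. Protocol 7.1 counts patients and SAP 5.6.1 records one result per patient. Protocol 6.4.2.2 says that "right and left lung will be tested independently" and 7.2 refers to each lung, but the SAP plans no per-lung analysis.

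**The minimum of 25 already permits 26.** True of Protocol 6.3.6 and SAP 5.1, and the gap is one patient. The stated 25 still does not deliver 22 evaluable at 15% drop-out.

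**Little depends on it.** Partly right. No threshold is set, the SAP plans intervals, and the rater table comes in addition to the OLV cross-correlation.

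**Conclusion.** The point holds as a mismatch between the stated power and the planned analysis. Protocol 7.1 claims 90% power to detect a difference from the reference without giving the test or the proportions; 7.2 requires a match; the SAP estimates per-patient rates with intervals. On the exact one-sample binomial reading that yields 22, the 0.9 is the chance of showing a shortfall if true accuracy is 0.9. In the direction of a match, exact per-patient power for a 0.1 difference is at most about 0.3 with a null of 0.5 to 0.9, and a perfect 22/22 does not exclude 0.90 (exact lower limit 0.846). Separately, 25 enrolled gives about 21 evaluable, not 22.

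A reader might infer that the subgroup is too small. The documents do not support that: no performance threshold exists to fall short of. The subgroup is also informative against guessing. With a null of 0.5, 17 of 22 correct suffices in a two-sided exact test, with power 0.90 if true accuracy is 0.85 (an assumed value). This is something the sponsor should correct; it does not threaten the trial.

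**What to change.** Keep the subgroup of at least 25 patients, and do one of the following.

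- **Preferred:** replace the power sentence for this endpoint with the precision of the planned per-patient intervals, and name the method. For example, with Clopper-Pearson: 22/22 correct gives a lower 95% limit of 0.846 and 20/22 gives 0.708; with 21 evaluable, 21/21 gives 0.839 and 19/21 gives 0.696.
- **Alternatively:** state the intended test and both proportions, and say what rejection would show. If 1.0 against 0.9 was meant, say that it detects a shortfall from a perfect reference.

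In either case, restate the evaluable number as 21 or the enrolled number as 26. It would also help to say whether the 15% covers patients who become drop-outs under the rater rules in SAP 5.6.1.

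The cost is a wording change in the protocol and SAP; restating the evaluable number as 21 adds no patients. The downside is a less favourable stated figure than 90% power for a 0.1 difference.

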6.3.6 NUMBER OF PARTICIPANTS

A sample size of n=80 patients (including at least 25 patients with OLV) has been calculated with an assumed drop-out rate of 15%.

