5 STATISTICAL ANALYSIS

5.1 PARTICIPANTS

A sample size of n=80 patients (including at least 25 patients for the OLV subgroup) has been calculated with an assumed drop-out rate of 15%.

OLV subgroup consists of patients who have been scheduled for surgical procedures that require the ventilation of only one lung (e.g., intubation using a double-lumen tube or placement of a bronchus blocker).

The remaining 55 patients are patients mechanically ventilated in an intensive care unit (ICU) via an artificial airway access (endotracheal tube or tracheostomy tube). For those, it can be assumed that significant changes to the ventilation settings will have to be made, which are continuously recorded with the PulmoVista 500 during the study.

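### Protocol 7.1 inflates the OLV subgroup differently from the primary endpoint (22 at 15% drop-out needs 26, not 25), and its 90% power is tied to no stated reference proportion or planned test

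*Protocol*

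**What the plan says.** Protocol 7.1 gives two sample-size statements, both at two-sided α = 0.05 and power 0.9.

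- **Primary endpoint:** "two-sided testing resulted in a sample size of 68 patients", inflated to 80 for 15% drop-out. The effect size (0.1 on the mean cross-correlation) and a standard deviation (below 0.25) are given.
- **OLV secondary endpoint:** "two-sided testing resulted in a sample size of 22 patients". The effect is described only as follows: "With this sample size a difference of 0.1 of the proportion between reference and investigated variable shall be detected". The enrolment figure is then "Accounting for 15 % potential drop-outs 25 patients shall be enrolled in this subgroup of the study".

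The status of the 25 varies. Protocol 6.3.6 says "A sample size of n=80 patients (including at least 25 patients with OLV) has been calculated with an assumed drop-out rate of 15", and SAP 5.1 likewise has "including at least 25 patients for the OLV subgroup". The Protocol synopsis and 7.7 give a plain 25. SAP 5.7 lists 25 as the planned OLV number beside 55 ICU patients, and SAP 5.1 also counts 55 as the remainder.

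On analysis, Protocol 7.2 compares EIT output with the clinical ventilation setting in a 2×2 table. SAP 5.6.1 derives a success rate, sensitivity and specificity from that table, each with a confidence interval. It also repeats the primary cross-correlation analysis in the OLV patients. Protocol 7.3 sets no pass/fail criteria.

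**The concern.** Two inflations in one section, at the same drop-out rate, do not follow the same rule. The primary figure divides by 0.85 and lands exactly on 80. The OLV figure does not reach its own target of 22 after the stated loss.

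The base figure of 22 also cannot be checked. The sample size for a difference of 0.1 in a proportion depends heavily on where the reference lies, and neither that value nor the test is stated. The SAP then analyses the 2×2 table by estimation, so the power figure describes no analysis that will be run on it.

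What is at stake is whether the OLV sample size can be traced and defended in the report. No primary result is affected.

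**Working it through.** **Inputs (Protocol 7.1):** primary N = 68 and OLV N = 22, both at two-sided α = 0.05 and power 0.90; drop-out 15%; enrolled 80 and 25; OLV effect 0.1 in a proportion. The OLV reference proportion and test are not stated.

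**1. Reproduce the primary figures.** One-sample t-test with standardised difference 0.1/0.25 = 0.4: the smallest n with power of at least 0.90 is 68 (power 0.902). Inflation: 68/(1 − 0.15) = 80.0. Both match.

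**2. Apply the same inflation to OLV.**
- 22/0.85 = 25.88, rounded up to 26.
- 25 × 0.85 = 21.25 expected evaluable; 26 × 0.85 = 22.1.
- Drop-out that 25 can absorb while keeping 22: 1 − 22/25 = 0.12, or three patients.
- Multiplying instead gives 22 × 1.15 = 25.3, which reaches 25 by rounding to nearest. The same rule gives 68 × 1.15 = 78.2 for the primary, not 80.
- If patients drop out independently at 15%, the binomial chance of keeping at least 22 is 0.47 with 25 enrolled and 0.65 with 26.

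**3. Size of the shortfall in power.** This needs an assumption, because the test is not stated.

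| Assumed basis | n = 22 | n = 21 |
|---|---|---|
| Exact binomial, reference about 1 against 0.9: 1 − 0.9^n | 0.902 | 0.891 |
| Normal approximation, scaled to 0.90 at n = 22 | 0.900 | 0.886 |
| One-sample t, scaled to 0.90 at n = 22 | 0.900 | 0.885 |

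The loss is about 1 to 1.5 points.

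**4. Where does 22 come from?** Exact one-sample binomial test, two-sided 0.05 (0.025 per tail), for a true value 0.1 below the reference:

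| Assumed reference | Rejects at n = 22 with | Power at n = 22 |
|---|---|---|
| 0.999 | 1 or more errors | 0.904 |
| 0.99 | 2 or more errors | 0.714 |
| 0.95 | 4 or more errors | 0.42 |

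Rejecting on any error at n = 22 has size 1 − p^22. That is 0.022 at p = 0.999, within 0.025, but 0.043 at 0.998 and 0.198 at 0.99. So this family gives 22 only for a reference of about 0.999 or higher.

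For a rise from 0.9 to 1.0 the exact two-sided test needs 36. The one-sample normal formula, two-sided, needs about 137 for 0.8 against 0.9 and about 259 for 0.5 against 0.6.

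A different family also gives 22: a two-sided one-sample t-test for a difference of 0.1 with an assumed standard deviation of 0.135 to 0.137. The documents do not settle which basis was used.

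**5. What the planned analysis can deliver.** If all n patients are classified correctly, the exact 95% lower limit for the success rate is 0.025^(1/n): 0.846 for 22/22 and 0.839 for 21/21.

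**The case against.** The best defence is that this is a rounding slip with no consequence. Protocol 6.3.6 and SAP 5.1 call 25 a minimum, so a 26th patient was never excluded. Power is stated to one decimal, and 0.891 rounds to 0.9. The endpoint is secondary, there is no pass/fail rule, and the lower confidence limit moves by less than one percentage point between 22 and 21 patients. In SAP 5.1 the 15% sentence has the total of 80 as its subject, and 80 is right, so that section contains no miscalculation of its own.

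Most of this stands and limits the size of the point. It does not remove it. Protocol 7.1 presents 25 as already covering 15% drop-out, which it does not, and the ICU remainder of 55 in the SAP treats 25 as the working number. SAP 5.6.1 also adds a way to lose patients: video sequences that the raters cannot assess, or on which they split after one abstains, become drop-outs.

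Two stronger readings are tempting, and the documents support neither.

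- **A reader might infer that the subgroup fails its stated 90% power.** That treats 25 as a ceiling and gives weight to about one power point, computed under a reference the protocol does not state.
- **A reader might infer that the power supports the opposite of the intended claim.** With a reference of about 100%, 1 − 0.9^22 is the chance of seeing at least one error when true accuracy is 0.9, which is power to reject perfect agreement. That reading reproduces 22, but it rests on an assumed reference of about 0.999 or higher. The t-test reading reproduces 22 equally well.

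**Conclusion.** The point holds as a minor inconsistency with a documentation gap beside it. By the rule that Protocol 7.1 uses for its primary endpoint, 22 evaluable OLV patients at 15% drop-out require 26 enrolled; 25 leaves about 21. This part rests on arithmetic alone. The consequence is one patient and about 1 to 1.5 power points, the latter depending on an assumed test.

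The second part is the more substantive. The stated power has no reference proportion and no named test, and SAP 5.6.1 tests no proportion. The OLV test it does plan is the primary-style comparison of mean cross-correlation with zero, a different quantity. The 22 therefore cannot be verified from the documents. Under exact binomial tests with less extreme references, a 0.1 drop would need more patients.

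Neither part affects the total of 80 or the primary analysis.

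**What to change.** 1. In Protocol 7.1, state either 26 OLV patients at 15% drop-out, or 25 with a 12% drop-out assumption. Carry the choice into the synopsis, 6.3.6 and 7.7.
2. Align SAP 5.1 and 5.7. With 26 OLV patients the ICU number becomes 54 and the total stays at 80. State once whether the OLV figure is a minimum or a target.
3. Replace the OLV power statement with the precision of the success rate that SAP 5.6.1 reports, for example an exact 95% lower limit of 84.6% if 22/22 are correct and 83.9% if 21/21 are. Sizing by precision is a design choice, but it matches the planned analysis. If the sponsor prefers to keep a power statement, it should give the reference proportion, the alternative and the test, and the SAP should plan that test.

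The cost is restated text. At most, one enrolment moves from ICU to OLV.
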